7.2 Study Procedures

(See section 7.4.1 for names and descriptions of investigative substances)

Overview: Microdialysis (MD) is a procedure in which a thin tube of membrane that mimics the capillary blood vessel is implanted in tissue. As a physiological saline perfuses the membrane, there is bi-directional exchange of molecules between the perfusing saline and the fluid bathing the tissue surrounding the membrane. However, the membrane prohibits the exchange of large molecules such as proteins. Substances of interest may be added to the perfusing saline and thus delivered into the surrounding tissues with no systemic effects.

All experiments occur in the morning.

Subjects fast for 8 hours prior to experiments so the data reflect the long term effects of the subject's diet over the previous 7 days rather than the short term effects of meals consumed just prior to experiments.

A. Screening

1. The participants drink only water and do not eat for 12 hours before the screening.
2. The research nurse conducts the screening that includes pregnancy test for women of childbearing-age, heart rate (HR), blood pressure (BP), height, waist circumference, weight, health history, and standard venipuncture to obtain blood (50 ml, <4 Tbsp) for complete blood count (CBC), chemistry analysis, lipid profile, and other substances of interest (i.e. Interleukin Panel).
3. If participant takes thyroid medication, the nurse obtains thyroid stimulating hormone (TSH) level from participant. If TSH level is not available or and has not been measured within 6 months, TSH is measured from blood sample (3.5 ml; 0.2 Tbsp).
4. The researchers do not perform genetic analyses on the blood nor look for presence of disease (e.g. HIV).
5. Subjects undergo ambulatory 24 hour blood pressure monitoring.

If the research nurse is unavailable for an extended period, the Clinical Research Center CRC staff performs her screening tasks. The CRC uses their admission form to admit potential participants for screening at the CRC.

Participants meet with a registered dietitian ([name], R.D.; PSU CTRC dietitian) to determine their eucaloric energy requirements and identify food preferences. The interview includes surveying the subject's physical activity over the previous 7 days. (This meeting can occur on a day separate from that of the screening.)

B. Baseline Experiments (Separate Days, the order of the local heating and acetylcholine dose response experiments is randomized)

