- c. Then the experiment is over, and we remove the MD tubing from the skin and place sterile bandages over the sites. If the subject desires, we can also place a bag of ice on the site for 10 minutes to reduce any bruising that may occur. We measure blood pressure and heart rate before the subject departs.

4. Baseline Experiments – “Day 2”

- a. MD: Acetylcholine (ACh) Dose Response

We prepare 5 MD sites:

- Probe 1. Lactated Ringer's only (control)
- Probe 2. Lactated Ringer's + LNAME
- Probe 3. Lactated Ringer's + Ascorbate
- Probe 4. Lactated Ringer's + Tempol
- Probe 5. Lactated Ringer's + Apocyanin

We clamp the temperatures of the local heaters at 34°C (93°F). When the experiment begins, the subject rests for a 20-minute baseline. When SkBF readings are stable, we add the test substances to probes 3, 4, and 5 as indicated above for about 60 minutes. After 30 minutes, we add LNAME to probe 2. During this time, we obtain a second baseline for about 20 minutes. When the SkBF is stable, we add the first concentration of ACh to the perfusate at each probe. Each site receives 11 increasing concentrations of ACh ($10^{-8}M$ to $10^{-1}M$) each perfused for 5 minutes. As SkBF stabilizes with the addition of each concentration of ACh, we proceed to the next concentration. After the last concentration of ACh, we switch perfusates at all sites to Ringer's + SNP for about 30 minutes. Heating and SNP perfusion causes maximum vasodilation.

- b. Then the experiment is over, and we remove the MD tubing from the skin and place sterile bandages over the sites. If the subject desires, we can also place a bag of ice on the site for 10 minutes to reduce any bruising that may occur. We measure blood pressure and heart rate before the subject departs.

5. Subjects wait at least 3 days before proceeding with the Controlled Feeding protocols.

C. Controlled Feeding Experiments (the order of the local heating and acetylcholine dose response experiments is randomized)

1. Feeding Protocol

Following baseline experiments outlined above, participants are enrolled in a randomized, cross-over protocol involving 4 controlled feeding periods, each 8 days in duration, (7 days prior to subsequent experiments plus the day

of first experiment). Subjects maintain the assigned feeding protocol through the 2 days of experiments. The feeding protocols are:

- low sodium diet devoid of dairy products (L-Na)
- low sodium diet containing cheese (L-Na+C)

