 - ii. Microdialysis probe insertion (described above)
 - iii. We attach 3 ECG leads to measure heart rate, and place a cuff on the upper arm sans the MD probes to measure blood pressure. We place a local skin heater and laser Doppler probe over each MD site. We measure heart rate, local temperature, and skin blood flow (SkBF) throughout the MD experiments. We also measure blood pressure every 5-7 minutes (brachial osculation and/or Cardiocap).

3. Experiments "Day 8"

- a. Subjects undergo 30 ml (2 Tbsp) blood draw to measure plasma oxidant stress and inflammatory markers.
- b. FMD (described above)
- c. MD Experiment - Local Heating (or Acetylcholine Dose Response) described above
- d. After the experiment, subjects resume the controlled feeding protocol. They eat as much of the food supplied for Day 8 as they can.

4. Experiments "Day 9"
 - a. MD Experiment - Acetylcholine Dose Response (or Local Heating) described above.
 - b. Subjects resume normal diet.
5. Subjects wait at least 3 days before beginning the next Controlled Feeding period. They undergo the 7-day Controlled Feeding periods followed by 2 days of experiments for each of the 4 feeding protocols. Subjects repeat the 3-day food record during one of the washout periods.

D. Equipment:

Laser Doppler Flowmetry: The Laser Doppler Flowmeter (Moor Instruments, Inc.) non-invasively provides a qualitative measure of skin blood flow to a depth of about 1 mm in the skin using a weak laser light. This measure is a dimensionless value called "flux" that reflects the speed and number of blood cells moving through the microvasculature in an area of skin. The flowmeter continuously measures skin blood flow using a fiber optic probes that fit into holders taped to the skin. approved by the FDA

Blood Pressure, ECG (Heart rate): The CardioCap 5 (General Electric – GE) critical care monitor measures blood pressure via a cuff inflated every 5-7 minutes on the upper arm and heart rate via 3-lead ECG probes taped to the skin of the chest. approved by the FDA

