14.0 Subject Stipend (Compensation) and/or Travel Reimbursements

Experiments (1 baseline + 4 controlled feeding periods = 5 of each type of experiment)

FMD/Sublingual Nitroglycerin:	\$250.00	\$50.00 each
MD local heating:	\$425.00	\$85 each (\$15.00 for each MD probe + \$25 for completing MD experiment)
MD ACh dose response:	\$575.00	\$115.00 each (\$15.00 for each MD probe + \$40 for completing MD experiment)

Bonus for completing all experiments: \$200.00

Total = \$1,450.00

For incomplete experiments, the researchers pay an amount of money equal to the part completed. For instance, if a subject completes half of an ACh dose response MD experiment, the subject receives \$15.00 for each MD probe inserted + \$20 (\$20.00 is one-half of \$40.00). The researchers may ask subjects to repeat a trial. If subjects agree to repeat a trial, they receive payment for the repeated trial as stated above. They are reimbursed for gasoline if they live more than 20 miles from Noll Lab.

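### The order of the two microdialysis tests is not stated to be fixed within a participant and no test-day term is planned, so a Day 8 versus Day 9 difference could add avoidable noise to the microdialysis diet contrasts

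*Combined protocol and SAP*

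**What the plan says.** Section 7.2 C describes the feeding phase as a four-period crossover ("participants are enrolled in a randomized, cross-over protocol involving 4 controlled feeding periods"). Its heading carries the only statement on test order in that phase: "Controlled Feeding Experiments (the order of the local heating and acetylcholine dose response experiments is randomized". Section 7.2 B says the same, separately, for the baseline experiments.

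The day-by-day schedule lets either test fall on either day. Day 8 lists "MD Experiment - Local Heating (or Acetylcholine Dose Response) described above" and Day 9 lists "MD Experiment - Acetylcholine Dose Response (or Local Heating) described above".

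The two days are not described alike:

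- **Day 8.** Before microdialysis the participant has a blood draw ("Subjects undergo 30 ml (2 Tbsp) blood draw to measure plasma oxidant stress and inflammatory markers") and FMD. The FMD block set out under baseline includes sublingual nitroglycerin, and the stipend table in section 14.0 pays for "FMD/Sublingual Nitroglycerin" as one item in all five rounds.
- **Day 9.** It follows a test visit that section 7.3 puts at under 7 hours, with an 8-hour fast beforehand and four or five probes inserted. After that visit, intake is as tolerated: "They eat as much of the food supplied for Day 8 as they can".

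Section 7.4.3, where a method of assignment would appear, is marked not applicable. Section 8.3 plans repeated-measures ANOVA with planned contrasts in PROC MIXED and names no term for test day or test order.

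**The concern.** The trial's precision rests on each participant serving as his or her own control. If a participant has the local heating test on Day 8 under one diet and on Day 9 under another, the difference between those diets also contains the difference between the days. With 15 completers, chance alone will not reliably balance test day across four diets. As written, neither the design nor the model removes such a day effect from the microdialysis contrasts. The trial already randomises the order, so it could remove the effect at almost no cost.

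**Working it through.** **Inputs from the documents.** Section 8.2 gives 14 subjects to detect a difference of at least 15% between diets (ANOVA, power 0.80, alpha 0.05) and proposes testing 15. No SD or within-person correlation is given.

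**Assumptions.** The 15% is read as 15 points on the outcome scale, and alpha as two-sided. Order is re-drawn 1:1 and independently in each period. The day effect is an additive shift of D points. The documents give no D, so values from 3 to 15 are shown.

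**The plan's own figure.** The 14 cannot be reproduced without an SD, so the SD was solved for. A paired t-test with n = 14, 15 points and 80% power implies an SD of within-person differences of 18.5 (variance 342.8). Other readings give different values: 20.0 by the normal approximation, and 16.2 from a four-level repeated-measures F test. The paired-t value is used below.

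**Added variance.** Write the test day under each diet as a 0/1 indicator with probability one half, so variance 1/4. The difference of two independent indicators has variance 1/2. A day shift of D therefore adds D²/2 to the variance of a two-diet difference.

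- D = 5: 25/2 = 12.5, and 12.5/342.8 = 3.6%. SD becomes √(342.8 + 12.5) = 18.85.
- D = 10: 100/2 = 50, and 50/342.8 = 14.6%. SD becomes √392.8 = 19.82.

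**Power at n = 15.** From the noncentral t with 14 degrees of freedom and noncentrality 15√15/SD:

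| D | SD of difference | Noncentrality | Power | N for 80% power |
|---|---|---|---|---|
| 0 | 18.52 | 3.14 | 83.1% | 14 |
| 3 | 18.64 | 3.12 | 82.6% | 15 |
| 5 | 18.85 | 3.08 | 81.7% | 15 |
| 7.5 | 19.26 | 3.02 | 80.1% | 15 |
| 10 | 19.82 | 2.93 | 77.8% | 16 |
| 15 | 21.34 | 2.72 | 71.7% | 18 |

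**The same quantity as imbalance.** The chance shift in a two-diet mean difference has SD D/√(2n): 5/√30 = 0.91 points at D = 5 and 10/√30 = 1.83 at D = 10. This is the same added variance on the standard-error scale, not a second harm. In head counts, the number tested on Day 8 differs between two given diets by 4 or more out of 15 with probability 20%.

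**Interaction contrast.** If Hypothesis 1a is tested as the sodium-by-cheese interaction, four indicators enter and the added variance is D². With an SD of 18.5 × √2 = 26.2 and a 15-point interaction, power is 54% at D = 0, 53% at D = 5 and 49% at D = 10.

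**Remedies, by simulation** (n = 15, 6,000 runs per cell, pooled error over all four diets, simulation error about half a point):

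| D | Order fixed | Re-drawn, no day term | Re-drawn, day term |
|---|---|---|---|
| 0 | 87% | 87% | 85% |
| 5 | 87% | 85% | 85% |
| 10 | 85% | 81% | 86% |
| 15 | 87% | 77% | 85% |

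The mean estimate stayed close to the true −15 in every cell, so there is no systematic bias. With order fixed, an additive day effect cancels exactly; the small movements in that column are simulation error. The day term recovers nearly all the loss when D is large, but costs a point or two when there is no day effect.

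**The case against.** **The unit of randomisation is not given.** A reader might infer that the plan re-draws the order within a person. The documents do not say so. One draw per participant for the whole feeding phase also fits the wording, and an additive day effect would then cancel. This stands, and the point is therefore conditional. But the text equally permits staff to re-draw each period, and no day term is planned for that case.

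**A day effect is conjecture.** The protocol says the diet is kept up through both experiment days, both tests follow the same 8-hour fast, and nitroglycerin is said to act for 5 to 10 minutes. Microdialysis delivery is described as local, and nothing says that Day 9 reuses the same sites. All of this is fair. It makes a large D less likely but does not rule one out, since as-tolerated intake and the previous day's probes remain.

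**Not all contrasts are exposed.** A reader might infer that every diet contrast suffers. That is not so. The blood draw and FMD are always on Day 8. Drug sites are run side by side in one visit, so a shift common to all sites also drops out of site-versus-control differences. Baseline is not one of the four diets, so its test order has no bearing on diet contrasts.

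**Randomising in each period is valid.** This is correct: it gives unbiased estimates, and with pooled error the simulated power at D = 10 is still about 81%. The issue is efficiency only.

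**Conclusion.** The point holds as a minor, nearly free improvement, not as an error in the plan. Section 7.2 C does not fix test order within a participant, section 8.3 has no test-day term, and the two days differ on the protocol's own description. If order is re-drawn in each period, a day effect costs precision in the microdialysis diet contrasts. At n = 15, power goes from 83% to 82% if the effect is 5 points, and to 78% if it is 10 points, which is two thirds of the 15-point target. These figures rest on an assumed D and on an SD back-solved from the stated sample size. A reader might go further and infer that the diet comparisons are biased; the documents do not support that, because random order leaves the estimates unbiased whatever the size of D.

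**What to change.** In section 7.2 C, state that the order of the two microdialysis tests is randomised once per participant, balanced across participants, and kept the same in all four feeding periods.

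Where order has already varied or will vary within a participant, record the test day and add it (8 or 9) as a fixed effect in the PROC MIXED model of section 8.3.

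The first change costs one sentence, with no added visits, procedures or participants. The second costs one degree of freedom and a little power if there turns out to be no day effect, so fixing the order is preferable where it is still possible. Fixing the order does not remove a day-by-diet interaction, and nor does a single day term.

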7.3 Duration of Participation

Screening (1 Visit)	less than 1.5 hour
FMD/MD Experiments (5 Visits)	less than 7 hours each
MD Experiments (5 Visits)	5 hours
Obtain Food, 24-hour BP monitor & urine container, etc. (~14 Visits)	about 15 minutes each

Total: ~75 Hours (~25 visits; It could take about 8 weeks to complete the study.)

7.4 Test Article(s) (Study Drug(s) and/or Study Device(s))

7.4.1 Description

Devices: See “7.2 Study Procedures”

Acetylcholine ACh Form: Powder
Role in Current Study: Local heating combined with the local perfusion of endothelial agonist, acetylcholine, specifically examines the attenuated endothelium-dependent vasodilation (eNOS-derived NO) associated with aging or vascular pathologies.

Apocynin Form: Powder
Role in Current Study: Apocynin inhibits NADPH oxidase, which is a primary source of superoxide production within the vasculature.

L-Ascorbate Vitamin C Form: Powder
Role in Current Study: L-ascorbate stabilizes norepinephrine in solution. A small amount will be delivered by MD to a nickel-sized are of skin.

Lactated Ringer's	Ringer's	Form: Liquid
Role in current study: Lactated Ringer's acts as the vehicle for the other research substances and as a flush.		
LNAME	N ^G -nitro-L-arginine methyl ester	Form: Powder
Role in current study: A nitric oxide synthase inhibitor. L-NAME is an analog to the amino acid, L-arginine. L-NAME is a non-specific inhibitor for nitric oxide synthases, thereby inhibiting the production of nitric oxide that causes vasodilation. We deliver small doses of LNAME to a nickel-sized area of the skin.		

Sodium Nitroprusside	SNP	Form: Powder
Role in Current Study: SNP, acting an NO donor, dilates blood vessels maximally thereby achieving maximal skin blood flow (SkBF). Maximal SkBF is a reference point for other measures of skin blood flow.		

Tempol	Form: Powder
Role in Current Study: Membrane-permeable scavenger of free-radicals. Tempol scavenges superoxide in vivo and reduces oxidant stress, acting as a superoxide dismutase mimetic. Tempol increases NO bioavailability in the vasculature and improves endothelial function. MD delivers a very small amount to the blood vessels in a nickel-sized area of skin.	

7.4.2 Treatment Regimen

Investigative Substances: Microdialysis

The following is a table of the research agents used with intradermal microdialysis. Based upon research literature, we use 14% for calculating maximum delivery of the research agents for all IND applications for our MD studies.

Research Agent	14% delivery (mg)
ACh	0.025
Apocynin	0.0005
Ascorbate	0.057
L-NAME	0.096
SNP	0.070
Tempol	0.00006

7.4.3 Method for Assigning Subject to Treatment Groups

NA

7.4.4 Subject Compliance Monitoring

Participants are to consume only those foods provided to them and to return any uneaten portions to accurately quantify food and beverage consumption. To ensure compliance and maintain effective rapport, participants visit the study center every 1-2 days to pick up food and drop off containers from the preceding 24-48 hours. Food intake is determined by weighing uneaten portions, and nutrient intakes calculated by a dietitian.

7.4.5 Blinding of the Test Article

NA

7.4.6 Receiving, Storage, Dispensing and Return

7.4.6.1 Receipt of Test Article

The containers of the substances are dated upon receipt and when opened.

Research Agent	Source(s)
ACh	USP
Apocynin	Sigma
Ascorbate	Sigma
L-NAME	EMD, Tocris
Lactated Ringer's	VWR, McKesson, Moore Medical
SNP	USP
Tempol	Calbiochem

From uploaded Physician Oversight SOP:

The investigative agents are purchased by the lab members from reputable sources as indicated in the IRB and the FDA IND applications and in accordance with the standards and guidelines imposed by the FDA. A license from the CRC

physician, the nurse manager, or the overseeing physician is filed with vendors (e.g. VWR, Owens and Minor) requiring the documentation for the purchase of some investigative agents (e.g. Lactated Ringer's). The investigative agents are shipped to the Noll Lab or picked up from the pharmacy by lab personnel. Copies of the prescriptions and orders are maintained in the laboratory's files.

7.4.6.2 Storage

Our procedures regarding the handling and use of the drugs have been extensively examined by the FDA and approved. The temperatures are recorded daily during weekdays. The temperature of the room is also monitored by the Central Control System of the Environmental Systems at PSU. The drugs used with microdialysis in their solid form are stored under environmental conditions according to manufacturer's instructions in cabinets, refrigerators, or freezers located in Room 224A or 228 Noll Laboratory. Opened drugs in their solid form are discarded after one year. The rooms are locked when unoccupied. General Note: The chemicals used for microdialysis in this study are scientific tools that are not FDA-approved, dispensable drugs, and do not have expiration dates. We purchase most of these chemicals in solid form. The chemicals are stable for years when stored according to manufacturer's instructions. Nonetheless, we purchase most of the chemicals in small vials that we typically exhaust within one to several weeks. Once mixed, we use stock solutions of the drugs within a week if stored in the refrigerator. We use solutions within 6 months if they are frozen. Final dilutions of solutions prepared for an experiment are used within a couple of minutes or hours of preparation.

7.4.6.3 Preparation and Dispensing

None of the microdialysis drugs are dispensed to the participant; rather we use them in the experiment, as outlined in the Standard Operating Procedures (Phys Ovrsght SOP). The physician providing oversight approves the laboratory standard operating procedure for the obtainment, preparation, and administration of all investigational agents for MD and other procedures used in experiments.

From uploaded Physician Oversight SOP:

Investigative Substances used with Microdialysis

The following procedures have been examined and approved by the FDA.

Trained lab personnel prepare the perfusates in accordance with the procedure described in the IRB and FDA IND applications. When mixing the perfusates, the experienced technician washes the hands, wears protection (e.g. gloves, lab coat), and uses glassware that has been washed with cleaner (designed for use with healthcare instruments, pharmaceutical process equipment, tissue culture apparatus, etc.), and rinsed multiple times in tap and then doubly-distilled water and air-dried. Most of the investigational agents are obtained in ultra-pure solid form. The solid investigational agents are weighed on a microbalance and then mixed with sterile pharmaceutical-grade Lactated Ringer's solution to the desired concentration. The solution is drawn into the syringe through a 0.2 µm filter. Prior to injecting a solution into or withdrawing solution from a sterile container through a sterile hypodermic needle, the stopper of the sterile container is cleaned thoroughly with alcohol. Most perfusates are used within minutes or hours after preparation. Stock solutions are made for some investigational agents. The stock solutions are drawn into sterile 1-cc syringes through 0.2 µm filters for storage. The sterile stock solutions are labeled accordingly (e.g. content, date), and protected from light. Stock solutions are not used beyond 1 week (refrigerated) and 6 months (frozen) after mixing. Stock solutions are diluted with sterile Lactated Ringer's when preparing the perfusate. The final dilutions of the perfusates are drawn into sterile syringes through 0.2 µm filters within minutes or hours of their use in the experiment. The protocol that includes the administration of the investigative substances has been examined and approved by the FDA.

The administration of the investigative substances is performed by the trained and approved lab personnel as described in the protocol included in the IRB and FDA IND applications. The overseeing physician has observed and approved the microdialysis technique as performed by Drs. [name] and [name]. The lab personnel performing microdialysis have been trained and approved to perform the technique by the [name], approved by the overseeing physician, and approved by the IRB. Letters of approval from the overseeing physician for each member of the lab who performs microdialysis in the researcher project have been submitted to the IRB.

